It is now clear that immunosuppressive strategies for renal transplantation achieve excellent short-term and medium-term results. Unfortunately, the long-term results have not substantially improved in the last 20 years. The reasons for this failure to achieve better long-term results are complicated and include such things as allowing older and sicker people to be recipients, using poorer quality donor kidneys and the complications associated with long-term immunosuppression. Among the worst of the long-term effects of chronic immunosuppression are the nephrotoxicity of the calcineurin inhibitors and the myriad complications of steroids. The goal of many now in the transplant field is to limit the exposure of transplant recipients to both steroids and calcineurin inhibitors. The following protocol evaluates the reduction of calcineurin inhibitors in a protocol that has already successfully eliminated the long-term use of steroids. Given the substantial experience with Campath® detailed above, the following study protocol will be offered to all patients undergoing renal transplantation at the University of Toledo University Medical Center. This is a small pilot study; multiple comparisons will be made for descriptive purposes only.

Hypothesis:

Our hypothesis is that conversion to everolimus (Zortress®), allowing the reduction of calcineurin inhibitors, will reduce nephrotoxicity (measured by increased creatinine clearance) and lengthen overall graft survival (measured by 2-year graft survival).

Objectives:

1. The primary objective of the study is to compare the efficacy and the effects on renal function of calcineurin-inhibitor reduction with conversion at 2 months after transplantation to Reduced Dose tacrolimus/everolimus in adult renal transplant recipients. Efficacy will be defined using two co-primary endpoints.
 - a. A composite efficacy end point [treated biopsy-proven rejection (BPAR), graft loss, death or loss to follow-up].
 - b. Renal function at 24 months post transplantation using GFR as measured by the Modified Diet Renal Disease (MDRD) estimation.

2. Secondary objectives will be to:
 - a. Compare the safety and tolerability of the experimental arm compared to the historical control arm.
 - b. Compare the presence of proteinuria as defined by spot urine protein to creatinine ratio greater than 1.0 in the experimental arm to the historical control arm.

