 - c. Compare the presence of hyperlipidemia in the experimental arm to the historical control arm.
 - d. Compare the incidence of impaired glucose tolerance (IGT) as assessed by fasting blood sugar, HbA1c and need for hypoglycemic medications in the experimental arm to the historical control arm.
 - e. Compare the incidence of mouth ulcers in the experimental arm to the historical control arm.
 - f. Compare the incidence of GI complaints including diarrhea in the experimental arm to the historical control arm.
 - g. Compare the incidence of leukopenia as defined by WBC less than 1.0, absolute neutrophil count less than 500 or the need for exogenous granulocyte stimulating factor administration in the experimental arm to the historical control arm.
 - h. Compare the incidence of thrombocytopenia at one year as defined by platelet count less than 50 or need to discontinue one of the study medications for more than 30 days in the experimental arm to the historical control arm.
 - i. Compare the incidence of neurotoxicity as defined by incidence of new onset seizure activity or tremors in the experimental arm to the historical control arm.
 - j. Compare the incidence of pneumonitis in the experimental arm to the historical control arm.
 - k. Compare the incidence of serious infections as defined by need for hospitalization in the experimental arm to the historical control arm.
 - l. Compare the incidence of CMV infection as defined by need for hospitalization in the experimental arm to the historical control arm.
 - m. Compare the incidence of BK infection as defined by blood titers requiring reduction in immunosuppressive dose in the experimental arm to the historical control arm.

n. Compare the incidence of BK nephropathy as defined by biopsy in the experimental arm to the historical control arm. Note that biopsies will not be required as part of the study but will only be done as part of the patient's standard of care if rejection is suspected (i.e. if the serum creatinine increases by 25% and is not associated with elevated tacrolimus levels or clinical signs of dehydration/illness to account for elevated creatinine).

o. Compare the incidence of malignancies including PTLN in the experimental arm to the historical control arm.

p. Compare the incidence of cardiovascular complications such as dysrhythmias, coronary artery disease requiring intervention or myocardial infarction in the experimental arm to the historical control arm.

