 - Adequate barrier methods of contraception include: diaphragm, condom (by the partner), intrauterine device (copper or hormonal), sponge or spermicide. Hormonal contraceptives include any marketed contraceptive agent that includes an estrogen and/or a progestational agent. Acceptable contraception methods will be discussed with all women of child-bearing potential.

- Reliable contraception should be maintained throughout the study and for 8 weeks after study drug discontinuation. For women who become pregnant while using Myfortic® or within 8 weeks of discontinuing therapy, we will report the pregnancy to the Mycophenolate Pregnancy Reference Registry ([name]) and will strongly encourage the patient to enroll in the pregnancy registry.
- Women are considered post-menopausal and not of child bearing potential if they have had 12 months of natural (spontaneous) amenorrhea with an appropriate clinical profile (e.g. age appropriate, history of vasomotor symptoms) or six months of spontaneous amenorrhea with serum FSH levels > 40 mIU/mL and estradiol < 20 pg/mL] or have had surgical bilateral oophorectomy (with or without hysterectomy) at least six weeks ago. In the case of oophorectomy alone, only when the reproductive status of the woman has been confirmed by follow up hormone level assessment is she considered not of child bearing potential.

Study Duration:

We plan to enroll 11 patients per year. Given this assumption, the enrollment will take five years. Adding two years of follow-up care, we will be able to complete the study in 7 years.

Study Design:

1. Single center pilot study utilizing historical control
2. A single treatment arm
3. Eleven patients per year
4. Five years to enroll 55 patients.
5. Enroll all patients who meet the inclusion criteria at 2 months and up to 6 months (± 10 days) post kidney transplantation and are willing to consent for this trial.
6. Patients would have study visits, serum creatinine measurements and other clinically relevant parameters measured monthly until 6 months, then q3 months until 2 years post-transplantation.
7. Graft survival would be measured by the absence of the need for dialysis.
8. It would not be mandatory, but a renal biopsy would be recommended at 2 years to look for underlying early signs of calcineurin toxicity/chronic allograft nephropathy.

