9. Secondary endpoints would include such parameters as post-transplant diabetes, proteinuria, lipid levels, mouth sores, neurotoxicity, pneumonitis, CMV, PTLN, BK-nephropathy, malignancies, cardiovascular complications, etc.
10. Our historical control will be composed of patients transplanted at the University of Toledo Medical Center between October 2011 and the beginning of this trial. All of those patients will have been treated with the exact same protocol as in this study except that they will not have been converted to the treatment arm above, but will have remained on tacrolimus and myfortic®, unless the clinical situation warranted changing immunosuppression. We expect that the control group will consist of approximately 50-55 patients and will have similar demographics to the patients that will be enrolled in this trial, given that we will use the same inclusion and exclusion criteria to select all patients from October 2011 until the start of this trial to populate

the historical control group. The reason for October 2011 as the starting point for the historical control is that this is the date when we modified our protocol to add a five day taper of steroids immediately after transplantation. Prior to that we only gave steroids immediately prior to the transplantation procedure. Thus, to be consistent with the patients in this trial, we believe the most accurate historical control should have the same treatment with steroids perioperatively. We will utilize all patients available in the historical control dataset and will not attempt to match for the demographics present in the experimental arm. The control group will consist of a historical control; prospective patients who are not willing to participate in the study will not be considered part of the control group.

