12. If delayed graft function is suspected, tacrolimus may be held for the first few days until the creatinine level begins to fall spontaneously.
13. Target tacrolimus levels for the first 2 months post-operatively will be 10-12 ng/ml with a target level goal of 10 ng/ml. After three months, the standard of care approach calls for the tacrolimus target level to be reduced to 8-10 ng/ml (with a target level of 8 ng/ml) until the end of the first year. After the first year, patients without evidence of rejection would have their tacrolimus dose reduced to achieve a trough level of 6-8 ng/ml (with a target level of 6 ng/ml). This approach was used for patients in the historical control arm.
14. No patients are to be treated for rejection without first obtaining a renal biopsy to confirm a cellular or humoral rejection.
15. Cellular rejections scored as Banff 1 will be treated with three, daily pulses of 250-500 mg methylprednisolone on three consecutive days and by confirming a therapeutic level of tacrolimus. Cellular rejections scored as Banff 2 or for those rejections that are not responsive to steroids alone, Thymoglobulin® will be used for a 10-14 day course. Depending on the level of rejection,

- ongoing steroid therapy can be administered after agreement by the treating physicians. Generally, hospitalization is required for at least the first few days of the treatment of rejection using Thymoglobulin®. During the first dose of Thymoglobulin®, blood pressure and vital signs will be monitored every 15 minutes for the first hour, then every 30 minutes for the next two hours, then every one hour for the next 3 hours and then per routine protocol if stable.
16. Humoral rejections will be treated with IVIG 100 mg/kg followed by a one volume exchange plasmapheresis on an every other day basis until the creatinine begins to fall or a decision is made to hold off on further treatment. In extreme cases, re-dosing Campath® can be considered or use of the anti-B cell agent, Rituximab (anti-CD20) can be used. These decisions will be made after consultation between the transplant surgeon and attending nephrologists.
 17. The intention-to-treat concept will be applied to patients who experience biopsy-proven rejection to avoid missing outcomes. For patients in the study, low-dose myfortic® may be added back to the patient's immunosuppression regimen. Short-term treatment with oral corticosteroids may be required, but long-term steroid use will be avoided.

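### The recommended 2-year biopsy contradicts the rule limiting biopsies to suspected rejection and, if controls had no such biopsy, could add a few silent events to the trial arm only

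*Combined protocol and SAP*

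**What the plan says.** **The biopsy rule.** Study Design item 8 makes biopsy non-mandatory but adds that "a renal biopsy would be recommended at 2 years to look for underlying early signs of calcineurin toxicity/chronic allograft nephropathy". That is a surveillance purpose. Objective 2n also says that the study does not require biopsies, but then that they "will only be done as part of the patient's standard of care if rejection is suspected", with a trigger of an otherwise unexplained 25% rise in serum creatinine. The visit schedule has no biopsy row. It does have a suspected acute rejection record at each visit.

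**The endpoints that depend on biopsy.** Co-primary endpoint 1a is "A composite efficacy end point [treated biopsy-proven rejection (BPAR), graft loss, death or loss to follow-up", with no time point and no condition on why the biopsy was done. Objective 2n is to "Compare the incidence of BK nephropathy as defined by biopsy" between the arms.

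**What follows a finding.** Item 14 of the detailed management protocol states: "No patients are to be treated for rejection without first obtaining a renal biopsy to confirm a cellular or humoral rejection". Item 15 states: "Cellular rejections scored as Banff 1 will be treated with three, daily pulses". Neither item mentions rejection found without a creatinine rise.

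**The controls.** Study Design item 10 describes them as "treated with the exact same protocol as in this study except that they will not have been converted to the treatment arm above". It does not say whether they had a 2-year biopsy.

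**The status of the comparison.** The Study Purpose section says that "multiple comparisons will be made for descriptive purposes only". The Statistical Section says that the study is not powered and that its data should be available for meta-analysis.

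**The concern.** An endpoint that exists only when tissue is taken depends on who is biopsied. If the trial arm is offered a biopsy that the controls were not offered, the trial arm can show more rejection and more BK nephropathy with no true difference between the regimens. Rejection is the main efficacy risk when a calcineurin inhibitor is reduced, so extra trial-arm events would fall where readers will look first.

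No formal test is at stake. But a one-directional difference in detection would travel with the data into any meta-analysis, and pooling reduces sampling error without removing it. If the reason for each biopsy is not recorded, a later reader cannot separate silent from clinical events.

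**Working it through.** **1. Is there a contradiction?** Not mandatory (item 8) and not required (Objective 2n) agree. Recommended at 2 years for surveillance and done only on suspicion of rejection do not.

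**2. Route to the endpoints.** BK nephropathy needs only the histological finding. The composite needs more: the patient accepts the biopsy, it shows rejection, the rejection is treated, and treatment falls before the cut-off. Items 14 and 15 make treatment after a positive biopsy a fair reading.

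**3. Timing.** Study Design item 6 ends visits at 2 years after transplantation. On that calendar the biopsy falls at the last visit and treatment would mostly come later. If the visit-schedule months instead run from a start 2 to 6 months after transplantation, the biopsy falls at study month 24 − 6 = 18 to 24 − 2 = 22, which leaves 2 to 6 months in which treatment would count.

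**4. Inputs.** From the documents: 11 patients a year × 5 years = 55 in the trial arm, as stated, and 50–55 controls. The documents give no uptake or yield, so the values below are assumptions. For the share of patients already with a composite event (p) I take 10–30%. The only local anchor is 19.8% two-year rejection in the centre's earlier tacrolimus/myfortic series, and it is rough: that series had no five-day steroid taper and included early rejections, which this trial excludes.

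**5. Added events if controls had no routine biopsy.** Added risk = uptake × yield × (1 − p); patients = 55 × added risk.

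| Endpoint, case | Uptake | Yield | p | Added points | Patients of 55 |
|---|---|---|---|---|---|
| Composite, low | 25% | 2% | 30% | 0.35 | 0.2 |
| Composite, middle | 50% | 5% | 20% | 2.0 | 1.1 |
| Composite, high | 75% | 10% | 10% | 6.75 | 3.7 |
| BK, low | 25% | 1% | 5% | 0.24 | 0.1 |
| BK, middle | 50% | 2% | 3% | 0.97 | 0.5 |
| BK, high | 75% | 5% | 0% | 3.75 | 2.1 |

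The composite rows assume that every counted rejection is treated before the cut-off. In the middle composite case the chance of at least one added event is 1 − 0.98^55 = 0.67. As an outer bound, 100% uptake, 15% yield and p = 10% would add 1.00 × 0.15 × 0.90 = 13.5 points (7.4 patients).

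**6. Against sampling error.** 95% half-width = 1.96 × √[p(1 − p)(1/55 + 1/m)], with m = 50–55 controls.

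- Composite: 11.2–11.5 points at p = 10%, 15.0–15.3 at 20%, 17.1–17.6 at 30%.
- BK nephropathy: 5.2–5.4 points at 2%, 8.1–8.3 at 5%.

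At 50% uptake and 5% yield the composite shift is 2.25 points at p = 10% and 1.75 at p = 30%, so 2.25/11.5 = 0.20 down to 1.75/17.6 = 0.10 of the half-width. The high case is 6.75/11.5 = 0.59 of it. The BK middle case is 0.97/5.2 = 0.19 down to 0.97/8.3 = 0.12.

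**7. If controls were also biopsied.** Net shift = (trial uptake − control uptake) × yield × (1 − p). With the middle composite inputs, control uptake of 25% gives 0.25 × 0.05 × 0.80 = 1.0 point, 50% gives 0, and 75% gives −1.0 point.

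**The case against.** The strongest case on the other side has five parts.

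- **BK nephropathy may already be protected.** The restriction to suspected rejection sits inside Objective 2n, the line that defines this endpoint. It can be read as confining the endpoint to for-cause biopsies. This stands as a possible reading; the text does not say so outright.
- **The composite route is a chain.** The surrounding text on rejection presupposes a creatinine rise, and silent rejection is not addressed. This stands as a reason for a conditional claim. It does not close the route, because nothing excludes such findings.
- **Timing.** If follow-up ends 24 months after transplantation, as co-primary endpoint 1b and item 6 suggest, the composite effect nearly vanishes. This stands. It does not help BK nephropathy in the same way, since that needs no treatment.
- **Direction.** A reader might infer that bias against everolimus is established. The documents do not support that. Objective 2n describes standard-of-care biopsy as for-cause, which makes routine control biopsies unlikely, but item 10 gives the controls the same protocol except for conversion. Step 7 shows that the net shift could be zero or reversed.
- **Size.** Every figure rests on assumed uptake and yield, in an unpowered descriptive pilot that already concedes the weakness of a historical control. This stands, and it limits the weight of the point.

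A reader might also infer that the eGFR co-primary is biased. It is not read from tissue, so the biopsy has no direct route to it. The missing biopsy row is weak evidence either way, since an optional procedure need not be scheduled.

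**Conclusion.** The contradiction between Study Design item 8 and Objective 2n is real and must be reconciled. The rest is conditional. If routine 2-year biopsies are done in the trial arm and were not done in the controls, silent findings can add trial-arm BK nephropathy (unless the Objective 2n note limits that endpoint to for-cause biopsies). They can add treated rejection only if treatment precedes the unstated cut-off.

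On that condition the bias runs against everolimus and would not create a false benefit. It is probably small: in the middle case 2.0 points, about 1 patient, for the composite, and 1.0 point, about half a patient, for BK nephropathy. Both are well inside sampling error. Only at the upper end of the assumptions does the shift become a large fraction of the half-width. The point is worth acting on because the remedy is cheap and the reason for a biopsy may be hard to recover later, not because the trial's conclusions are in danger.

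**What to change.** 1. Reconcile Study Design item 8 with Objective 2n. No rule on who is biopsied or treated is proposed here.
2. Record the reason for every biopsy in the trial arm, and check the control charts for biopsy reasons, including any routine 2-year biopsy.
3. Base the between-arm comparison of the composite and of BK nephropathy on all clinically indicated biopsies in both arms: suspected rejection, raised creatinine, BK titers or another clinical reason. Leave out only findings made solely on a routine 2-year biopsy. A narrower definition, suspected rejection alone, would drop genuine BK cases, because BK titers are monitored and item 18 of the detailed management protocol lists BK nephropathy among the non-rejection causes of raised creatinine.
4. Report both endpoints with and without the findings left out.
5. State one composite cut-off and apply it to both arms, after settling whether the visit-schedule months run from transplantation or from study start.

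**Cost.** A few sentences, one data field, and a review of 50–55 control charts. The small downside is that silent rejection moves to a supplementary report, where the with-and-without presentation keeps it visible.
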